#### **10.3. Procedures for Recording Adverse Events**

The safety profile of Adalimumab is well known, with the most common adverse reactions being mild injection site reactions (see section 4). Common Terminology Criteria for Adverse Events (CTCAE) v4.0 (U.S. Department of Health and Human Services) will be used to guide recording Adverse Events including grading of the event.

**Part 1.** All AEs graded 3 and above occurring during the trial and until 12 weeks **after surgery** that are observed by the Investigator or reported by the participant will be recorded on the CRF, whether or not attributed to trial medication.

**Part 2.** All AEs graded 3 and above occurring during the trial until 28 days after the last injection of trial medication that are observed by the Investigator or reported by the participant and are attributed to trial medication or the injection of the trial medication will be recorded on the CRF. The capture all of AEs in the trial CRFs is deemed not necessary due to the period of time for which the IMP has had a marketing authorisation and it's well established safety profile.

The following information will be recorded: description, date of onset and end date, severity, reason for seriousness, assessment of relatedness to trial medication, other suspect drug or device and action taken. Follow-up information should be provided as necessary.

AEs considered related to the trial medication as judged by a medically qualified investigator will be followed either until resolution, or the event is considered stable.

It will be left to the Investigator's clinical judgment to decide whether or not an AE is of sufficient severity to require the participant's removal from treatment. A participant may also voluntarily withdraw from treatment due to what he or she perceives as an intolerable AE. If either of these occurs, the participant must be given appropriate care under medical supervision until symptoms cease, or the condition becomes stable.

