### Part 1. Dose response

For the dose response, study participants will be recruited with **established DD** who are scheduled for surgery for excision of the diseased tissue to correct flexion deformities of the fingers, to assess the efficacy of adalimumab in down regulating the phenotype of myofibroblasts. A maximum of 40 participants will be randomised to participate in the study if they meet the inclusion criteria and provide written consent. All participants will be screened for TB, Hepatitis B and C and HIV. If results are positive for any test, the participant will not be eligible to enter the trial and will be informed and counseled about the result of their test. Consented participants will enter the trial and receive the injection(s) two weeks prior to the scheduled surgery date. Intra-nodular injections will be delivered into the most prominent nodule due to be excised by surgery. If participants do not proceed to surgery at 12-18 days following injection, the reason will be recorded and they will continue with normal care. These participants may be replaced if still during the recruitment phase of the dose response study.

The diseased tissue excised during surgery, which would normally be discarded as waste, will be collected and analysed centrally for  $\alpha$ -SMA, COL-1A1, COL-3A1 and cadherin 11 mRNA expression, and  $\alpha$ -SMA and, where sufficient material exists, collagen protein levels. As other markers and assays of myofibroblasts become available these may also be used. The primary outcome measure will be mRNA for  $\alpha$ -SMA measured using RT-PCR for doses of adalimumab compared to equivalent volumes of saline.

Study participants will be seen at 4 time points after screening: week 0, week 2, week 2 post-surgery and week 12 post-surgery according to the summary chart (Appendix A). The schedule, duration of each visit and visit window is detailed in the Schedule of procedures (Appendix C: Schedule of procedures Part 1).

The safety profile of adalimumab is well known; with the most common adverse reactions being mild injection site reactions (see Section 4 Background). Participant safety will be monitored for three months after surgery, and if more than one participant in a dose cohort has an unplanned admission to hospital or unplanned surgery related to the surgery for Dupuytren's disease of the affected digit, or if any participant experiences a SUSAR, we will refer for advice to the Safety Committee.

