Participants may withdraw from the study at any time and will continue normal NHS clinical care. Information collected up to the point of withdrawal may still be used. To monitor safety, if the participant withdraws after they have received the medication their medical notes may be reviewed for 3 months after the baseline visit. Samples donated by participants for research are difficult to destroy on request once samples are processed for storage. Participants will be informed that they will not be allowed to request their samples to be destroyed at a later date.

The first participants will be recruited to 15 mg (in 0.3 ml carrier) and 35 mg (in 0.7 ml carrier) intra-nodular adalimumab cohorts. Each of these cohorts will initially recruit eight participants, of which two participants in each cohort will be assigned to placebo. A further eight participants will be recruited to a 40 mg (in 0.4 ml carrier) intra-nodular adalimumab cohort, with two participants in this cohort assigned to placebo.

Interim analyses of the excised disease tissue may be used to guide further decisions on cohort size and dose selection. However, the frequency of interim analyses is limited by the necessity for samples to be compared within each analysis run. The Trial Management Group (TMG) will monitor recruitment and will recommend the points at which any interim analyses will be performed.

Blinded data from interim analyses, together with safety data, will be presented to the Safety Committee for a decision on how best to proceed with the study. All decisions on cohort size and dose selection will be documented in the TMF. The Safety Committee may recommend to stop the dose response study at this point, to increase the participant numbers (either for all or specific cohorts), or to collect data at (an)other dose(s). Decisions on dose cohorts will adhere to the following rules:

- A maximum of 40 participants will be recruited
- The dose administered into the nodule will not exceed 80 mg adalimumab or 0.8 ml in volume.

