#### **Part 1 Dose response**

One week after treatment participants will be phoned by a hand therapist, Investigator or other member of site staff to monitor for adverse events. Any concerns raised by this call will be brought to the urgent attention of the site PI or other Investigator on the site delegation log promptly.

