#### **Visit 5 (12 weeks after surgery) (15 minutes) + standard consultation time**

Following the standard care pathway following surgery for DD, participants will be reviewed in the outpatient hand clinic.

- Review of possible adverse events.
- Participants will complete a Health Quality of Life Questionnaire, the EQ-5D-5L.

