#### **8.9. Definition of End of Trial**

The end of trial for each part of the study is the date of the last visit of the last participant. The overall end of the trial is the last visit of the last participant in part 2, or if the last participant is unable/unwilling to attend, the date of receipt of their completed questionnaires.

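### Part 1 adverse events are to be recorded to 12 weeks after surgery, but the last scheduled trial contact may validly take place at week 8, with nothing required afterwards

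*Protocol*

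**What the plan says.** **Recording period.** Protocol section 10.3 covers, for Part 1, "All AEs graded 3 and above occurring during the trial and until 12 weeks" after surgery, regardless of attribution to the study drug. The Synopsis also gives Part 1 follow-up as 12 weeks after surgery.

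**Monitoring period.** Section 6, Part 1, states: "Participant safety will be monitored for three months after surgery". Section 11.5 opens its Part 1 paragraph the same way. Both go on to say when the Safety Committee is consulted about unplanned admissions or unplanned operations related to the Dupuytren's surgery. Section 6 requires two or more affected participants in the same dose cohort; section 11.5 requires only one participant.

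**Contacts.** Section 6 lists the visits after screening as "week 0, week 2, week 2 post-surgery and week 12 post-surgery". Section 8.6 adds one telephone contact: "One week after treatment participants will be phoned by a hand therapist, Investigator or other member of site staff to monitor for adverse events". That call comes before surgery. The final visit is headed "Visit 5 (12 weeks after surgery) (15 minutes) + standard consultation time" and includes an adverse event review. Appendix C gives it a window of 4 weeks either side. Section 8.9 adds: "The end of trial for each part of the study is the date of the last visit of the last participant".

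**Withdrawn participants.** After a participant who has been injected withdraws, section 6 says "their medical notes may be reviewed for 3 months after the baseline visit". Section 8.8, in text covering both parts, instead allows notes review over the normal length of follow-up, to capture events of grade 3 or above.

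**The concern.** The period over which events are to be recorded is fixed from surgery, but the visit that would close it can move four weeks earlier. The protocol does not say that Visit 5 must wait until the recording period has ended, and it requires no contact after an early Visit 5. Under section 8.9, Part 1 could even end formally on a week-8 visit of its last participant, before that person's recording period is over.

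What is at stake is the completeness of the Part 1 safety data. The Safety Committee uses those data, with the interim tissue results, to advise on cohort size and dose. The initial cohorts have eight participants each, six on adalimumab and two on placebo, so single events carry weight.

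**Working it through.** The plan states no figure for this gap. The check is date arithmetic.

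**Inputs**
- End of recording: 12 weeks (84 days) after surgery (Synopsis; section 10.3).
- End of monitoring: three months after surgery (sections 6 and 11.5). Three calendar months are 89 to 92 days, depending on the start date.
- Visit 5: week 12, 4 weeks either side (section 8.6; Appendix C).
- Surgery: 12 to 18 days after injection (section 6).
- Serious adverse event reporting: to 28 days after the last injection, related events only (section 10.4). Part 1 has one injection.

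**1. Earliest and latest Visit 5.** 12 − 4 = week 8 (day 56 after surgery); 12 + 4 = week 16.

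**2. Gap after a week-8 visit**
- Against the recording period: 12 − 8 = 4 weeks, and 4/12 = 33%.
- Against three calendar months: 89 − 56 = 33 days to 92 − 56 = 36 days, that is 4.7 to 5.1 weeks. In round weeks, 13 − 8 = 5, and 5/13 = 38%.

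**3. Gap after a Visit 5 exactly on time (day 84)**
- Against the recording period: none.
- Against three calendar months: 89 − 84 = 5 days to 92 − 84 = 8 days.

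**4. Average gap to week 12.** The documents do not give actual visit dates. Assume, for illustration, that visits are spread evenly from week 8 to week 16.
- Half then fall before week 12.
- Mean gap among those: (4 + 0)/2 = 2 weeks.
- Mean gap over all participants: 0.5 × 2 + 0.5 × 0 = 1 week.

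If visits cluster near week 12, both averages are smaller. The 4-week maximum for an in-window visit does not depend on this assumption.

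**5. Does serious event reporting fill the gap?** It closes 28 − 18 = 10 to 28 − 12 = 16 days after surgery. It therefore does not reach weeks 8 to 12.

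**6. Withdrawn participants, counted from baseline**
- Section 6: three months, about day 91.
- Section 8.8 with the Synopsis: 12 + 84 = day 96 to 18 + 84 = day 102.
- Difference: 96 − 91 = 5 to 102 − 91 = 11 days.

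**7. Effect of one missed event on referral**
- Section 11.5 wording: one missed event is enough to change whether the committee is consulted, if no other has occurred.
- Section 6 wording: one missed event changes this only if exactly one other participant in that cohort is already known to have had an event.

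**The case against.** A symmetric window around a nominal final visit is ordinary practice, and a closing call is partly a design choice. Section 10.3 also accepts events that participants report themselves, so it does not rest on a final visit alone. Participants remain in post-surgical care: Visit 5 is combined with the hand clinic, and the Background says patients need 3 to 6 months of hand therapy. An admission or reoperation related to the Dupuytren's surgery would probably come to the treating team's notice. All of this stands, and it limits the harm. It does not supply a scheduled trial contact or an instruction to look.

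A reader might infer more than the documents support in four respects:

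- **That events after week 8 are lost.** They are not actively sought, which is different. The gap is in scheduled trial contact.
- **That five weeks are missing from the recording rule.** Five weeks applies only if three months is a separate requirement. It may be a loose description of the 12-week follow-up. The explicit recording rule leaves at most four.
- **That the notes of withdrawn participants cannot be reviewed to 12 weeks after surgery.** Section 8.8 already permits this. The fault is that section 6 says something shorter.
- **That the comparison of active and placebo is biased.** Section 5 defines Part 1 adverse event assessment by contact, at research visits, the one-week call and the injection and surgery site checks. Section 11.2 specifies no time-at-risk analysis. The window is the same in both arms and assessors are blinded, so the documents give no reason to expect capture to differ by arm.

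**Conclusion.** The mismatch is real but minor. A Visit 5 held in window at week 8 leaves 4 of the 12 recording weeks without scheduled trial contact, or about 5 weeks of a literal three months. The averages of 2 weeks among early attenders and 1 week over everyone rest on the assumed even spread of visits; the true loss depends on visit dates that the documents do not give. The reading also takes the three windows in the Appendix C Part 1 schedule as belonging, in order, to Visits 3, 4 and 5.

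Two related conflicts need resolving at the same time: the length of notes review after withdrawal (section 6 against section 8.8) and the number of affected participants that prompts referral (section 6 against section 11.5). This review takes no position on which threshold is right.

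The consequence is confined to the completeness of Part 1 safety data. Neither the Part 1 mRNA outcome nor any Part 2 result is affected.

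**What to change.** Reconcile Protocol sections 6, 8.6, 8.8, 10.3, 11.5 and Appendix C to one Part 1 safety end date of the sponsor's choosing, and apply it to notes review of withdrawn participants as well. State that when Visit 5 falls before that date, grade 3 or higher adverse events and unplanned admissions or operations are sought by a short telephone call or a notes check once the date has passed. Reconcile the referral threshold in sections 6 and 11.5.

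If Part 1 follow-up is already complete, the equivalent step is a notes check for those seen early, or a statement in the report of the follow-up time actually achieved.

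The cost is protocol wording and one brief call or notes check per early attender, for at most 40 people.

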#### **10.4. Reporting Procedures for Serious Adverse Events**

SAEs occurring after the first injection of trial treatment and up to 28 days after the last injection of trial treatment must be reported to the RIDD Trial Office. Only SAEs that are related to trial medication or the injection of the trial medication require to be reported. The reporting of SAEs not related to the IMP/injection is deemed not necessary due to the period of time for which the IMP has had a marketing authorisation and it's well established safety profile.

SAEs must be recorded on the trial specific SAE form and reported within 24 hours of the Site Study Team becoming aware of the event. Causality must be assessed by a medically qualified doctor. The SAE form must be sent to the Trial Office. Details are as follows:

Trial Office contact: [contact] [contact]

The Trial Office will review the information on the SAE and raise immediate queries for any key data which is missing. In the event where the reporting site does not provide an assessment of causality the Trial Office will assume that the event is related to the IMP.

The SAE form will also be sent to an independent clinician as soon as all the relevant information is available but no later than 3 calendar days from when the Trial Office is made aware of the event as per OCTRU SOPs for safety reporting. The independent clinician will assess the SAE for causality and expectedness and provide a response as per OCTRU safety reporting. In the event where the independent clinician disagrees with the assessment of the site PI, a discussion will be encouraged between the two to re-assess the event. If either the PI or the independent clinician continue to assess the event as related, both assessments will be recorded. If the event is also related and unexpected this will be reported as a SUSAR by the Trial Office or delegate to the relevant Competent Authorities, UK Ethics, Sponsor and other bodies in with the nation and local regulations of participating sites, as per below.

All SAEs will be followed till resolved or no further information is expected. SAEs will only be considered closed when signed off by the local PI.

SAEs will be reviewed at the next Safety Committee meeting (Part 1) or Data and Safety Monitoring Committee meeting (Part 2).

#### **10.5. Expectedness**

Expectedness will be determined by the independent clinician according to the reference safety information (RSI) section of the Summary of Product Characteristics of for the 40 mg solution for injection in pre-filled syringe.

#### **10.6. SUSAR Reporting**

All SUSARs will be reported by the Trial Office or delegate to the relevant Competent Authorities, UK Ethics, Sponsor and other bodies in line with the nation and local regulations of participating sites, as applicable. For fatal and life-threatening SUSARs, this will be done no later than 7 calendar days after the Sponsor is first aware of the reaction. Any additional relevant information will be reported within 8 calendar days of the initial report. All other SUSARs will be reported within 15 calendar days.

Treatment codes will be un-blinded for specific participants.

## **10.7. Development Safety Update Reports**

The Development Safety Update Reports will be prepared by the CI and submitted to the relevant Competent Authorities, UK Ethics, Sponsor and other bodies in line with the nation and local regulations of participating sites, and to the Sponsor within the timelines as per the relevant OCTRU SOP.

## **11. STATISTICS**

Full details of the statistical analysis will be detailed in a statistical analysis plan (SAP) which will be finalised prior to any data analysis.

Stata (StataCorp LP) or other appropriate validated statistical software will be used for analysis.

### **11.1. Inclusion in Analysis**

The intention-to-treat population is all randomised participants, grouped by the treatment allocated as opposed to the treatment received.

The per-protocol population includes those participants who complied with the protocol in terms of eligibility, treatment and availability of outcome measurements. Full details of the exclusions from this population will be detailed in the SAP.

The safety population is made up of all participants who started treatment, that is, who received at least one injection.

### **11.2. Description of Statistical Methods**

During the dose response ([Part 1](#)), analysis will be carried out using data from all participants randomised to Part 1. In the RCT ([Part 2](#)), all analyses will be performed on participants randomised to Part 2 only, on an intention-to-treat basis with sensitivity analyses run on the per protocol population.

#### **Part 1**

Descriptive statistics will be used to describe the demographics between the intervention groups for each dose. This difference in the mean between cases and controls will be reported with 95% confidence intervals for all continuous outcome variables. P-values will be reported to 3 decimal places.

The primary outcome measure for [Part 1](#) is expression of mRNA for  $\alpha$ -SMA. Expression will be quantified with PCR using the standard curve method using GAPDH, B2M and PGK1 as housekeeping genes to normalise the samples.

The secondary outcome measures to be analysed include expression of mRNA for COL-1A1, COL-3A1, adherin 11 and levels of  $\alpha$ -SMA and collagen proteins, nodule size and nodule hardness.

For continuous variables, the difference in the means and the corresponding 95% confidence interval will be reported for each dose group and overall. For categorical variables, the number (and percentage) of participants in each category will be reported for each dose group and overall.

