#### **5. OBJECTIVES AND OUTCOME MEASURES**

**See Appendix C for schedule of procedures and visit windows**

**Research hypothesis:** To determine whether experimental treatment by injection with adalimumab will control the progression of early Dupuytren's disease more than control placebo treatment by injection with normal saline.

Part 1. Objectives	Outcome Measures	Timepoint(s) of evaluation of this outcome measure (if applicable)
Primary Objective To establish an effective dose of adalimumab for down regulating the myofibroblast phenotype in participants with Dupuytren's disease.	Expression of mRNA for $\alpha$ -SMA from participants on each treatment.	Analysis of tissue removed during surgery at 12-18 days post-treatment.
Secondary Objectives To determine the effectiveness of adalimumab for myofibroblast inhibition in participants with Dupuytren's disease and nodules.	For participants on each treatment 1. Expression of mRNA for COL-1A1, COL-3A1 and cadherin 11 2. Levels of $\alpha$ -SMA and collagen proteins. 3. Hardness of selected nodule 4. Ultrasound imaging of nodule size.	1 and 2. Analysis of tissue removed during surgery at 12-18 days post-treatment. Measures 3 and 4 measured before treatment and at 2 weeks post-treatment.
Monitor for adverse events	Adverse event assessment comparing active and placebo groups using visual inspection of injection site, surgery site and laboratory reports.	Observation at each research visit. Injection site assessment immediately after injection and 2

		weeks later. Health check phone call 1 week post treatment. Surgery site assessment at 2 weeks post-surgery.
To assess whether adalimumab affects the healing of the surgical incisions or subsequent scarring.	Visual assessment of surgical wounds using hand photographs of all participants on each treatment.	2 and 4 weeks post surgery.
Tertiary Objectives To determine circulating levels of adalimumab and antibodies to adalimumab in the blood.	Circulating levels of adalimumab and antibodies to adalimumab in the blood.	Analysis of blood samples taken pre-injection and at 2 weeks post-treatment.

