#### **8.4. Randomisation, blinding and code-breaking**

For Part 1 and Part 2, randomisation will be undertaken prior to or at the baseline visit prior to receiving the trial injection. The randomisation procedure and allocation ratios for the two parts of the trial will differ:

**Part 1:** participants will be randomised 1:3 to placebo or adalimumab within each dose cohort. Each participant will be assigned a Trial ID as they enter the study. Pharmacy will refer to the allocation log, which is securely stored in pharmacy, to ensure they dispense the IMP corresponding to the Trial ID. To enable unblinding, the randomisation will retrospectively be added to the RRAMP system (see below) by an unblinded member of the trial team.

**Part 2:** participants will be randomised 1:1 to placebo or adalimumab with stratification by age and centre. Participants will be randomised through a secure online service provided by the Oxford Clinical Trials Research Unit (OCTRUE) called RRAMP. RRAMP is used to randomise participants and this will generate a Trial ID and prompt an email to Pharmacy which informs them of which IMP (drug or placebo) to dispense.

The randomisation procedures will be fully documented, reviewed, tested and approved prior to the start of the study.

The methods for blinding will be influenced by the packaging of the adalimumab being used. Where possible the adalimumab will be supplied in a single use glass vial. However, a pre-filled syringe may be the only option if using the 40 mg in 0.4 ml formulation (see section 9.1).

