#### **Part 2**

The primary outcome measure is change in nodule hardness from baseline to 12 months. There will only be one dose level used in **Part 2**, which will be 40 mg of adalimumab. It is expected that all nodules will be large enough to accommodate the injection, but if not the volume of residual IMP will be recorded. The difference in the mean change of nodule hardness between the two groups will be reported with 95% confidence intervals. The comparison of change in nodule hardness between interventions will be analysed primarily using Analysis of Covariance (ANCOVA) adjusting for baseline nodule hardness, if it is normally distributed. As a secondary confirmatory analysis, ANCOVA adjusting for baseline nodule hardness as well as the stratification factors which are centre (Oxford, Edinburgh or Groningen) and age group (18-49 or  $\geq$  50 years) will be conducted.

If the data are not normally distributed, the data will be log-transformed in order to gain normality and geometric means with 95% confidence intervals will be reported. If data are not normally distributed after log-transformation, the non-parametric Mann Whitney test will be used with no adjustment for baseline, and the median change with 95% confidence intervals will be reported.

In order to analyse change in nodule hardness over the full time period, linear mixed effects regression will be used to compare nodule hardness between interventions utilising all time-points up to 18 months and adjusting for stratification and other important prognostic factors.

The secondary outcome measures for **Part 2** include those for **Part 1** and also grip strength, range of motion and participant reported outcomes.

For nodule size, grip strength, range of motion of the affected digit, Michigan Hand Outcomes Questionnaire, patient identified activity most restricted by DD, progression to surgery, and injection experience linear mixed effects regression models will be used. This procedure will allow for data from all follow-up time-points to be accounted for, and for adjustment for baseline measures to be made. The time (days) between baseline injection and each follow-up time-point will be included in the models as a random effect to account for patients not all having their follow-up assessments at the same time.

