## 1.2 Changes from previous version of SAP

A summary of key changes from earlier versions of SAP, with particular relevance to protocol changes that have an impact on the design, definition, sample size, data quality/collection and analysis of the outcomes will be provided. Include protocol version number and date.

Version number Issue date	Author of this issue	Protocol Version & Issue date	Significant changes from previous version together with reasons
V1.0_30Nov2015	[name]	Protocol_V4.0_13Aug2015	Not applicable as this is the 1 st issue
V1.5_21Sep2016	[name]	Protocol_V8.0_19Aug2016	
Part 1 – dose choice: The choice of dose cohorts in Part 1 will be decided by the Safety Committee following analysis. No cohorts will use systemic injections.
 
Part 1 - secondary objectives:
 
Expression of collagen type I and <math>\alpha</math>-SMA protein in excised nodule tissue have been added.
 
Grip strength, range of motion, the Michigan Hand Outcomes Questionnaire (MHQ) and activity most restricted have been removed to reduce patient burden and encourage recruitment.
 
Part 1 – fewer study visits:
 
The study visit one week after injection will be replaced with a phone call. The study visits one and four weeks after surgery have been removed.
 
Inclusion/exclusion criteria – Updated in line with protocol.
 
Part 2 – dose choice: New formulation of adalimumab has been released (40mg in 0.4ml into the nodule) and therefore a new dose cohort was included.

V2.0_07Jan2021	[name]	Protocol_V13.0_21Nov2019	Restriction of analysis plan to include only RIDD part 2.

Repurposing anti-TNF for treating Dupuytren's disease (funded by Health Innovation Challenge Fund, Wellcome Trust)  
EudraCT Number: 2015-001780-40 and OCTRU Reference Number CTU0028

Version number Issue date	Author of this issue	Protocol Version & Issue date	Significant changes from previous version together with reasons

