## 11. APPENDIX 2: RIDD PART 1; STATISTICAL ANALYSIS OUTLINE (FROM PROTOCOL)

During the dose response (**Part 1**), analysis will be carried out using data from all participants randomised to **Part 1**.

Descriptive statistics will be used to describe the demographics between the intervention groups for each dose. This difference in the mean between cases and controls will be reported with 95% confidence intervals for all continuous outcome variables. *P*-values will be reported to 3 decimal places.

The primary outcome measure for **Part 1** is expression of mRNA for  $\alpha$ -SMA. Expression will be quantified with PCR using the standard curve method using GADPH, B2M and PGK1 as housekeeping genes to normalise the samples.

The secondary outcome measures to be analysed include expression of mRNA for COL-1A1, COL-3A1, aherin 11 and levels of  $\alpha$ -SMA and collagen proteins, nodule size and nodule hardness.

For continuous variables, the difference in the means and the corresponding 95% confidence interval will be reported for each dose group and overall. For categorical variables, the number (and percentage) of participants in each category will be reported for each dose group and overall.

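### Part 1 nodule hardness and size have a pre-injection value, but the planned analysis names neither change from baseline nor baseline adjustment, which gives up precision in very small cohorts

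*Protocol*

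**What the plan says.** Protocol section 5 lists hardness of the selected nodule and ultrasound nodule size as the third and fourth measures under the first Part 1 secondary objective. On timing it says "Measures 3 and 4 measured before treatment and at 2 weeks post-treatment". The Part 1 schedule in Appendix C agrees.

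Protocol section 6 sets the cohort size: "Each of these cohorts will initially recruit eight participants, of which two participants in each cohort will be assigned to placebo". The 40 mg cohort has the same split, and section 8.4 confirms that "participants will be randomised 1:3 to placebo or adalimumab within each dose cohort". The comparator is stated for the mRNA primary outcome, "for doses of adalimumab compared to equivalent volumes of saline", which implies 6 v 2 within each cohort.

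Protocol 11.2 (Part 1) names nodule size and hardness among the outcomes to be analysed and then gives one rule for every continuous variable: "For continuous variables, the difference in the means and the corresponding 95% confidence interval will be reported for each dose group and overall". SAP Appendix 2 repeats that "the difference in the means and the corresponding 95% confidence interval will be reported for each dose group and overall", but its heading says it is taken from the protocol. The SAP change table records "Restriction of analysis plan to include only RIDD part 2".

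For Part 2, the same Protocol section defines the primary outcome as change in hardness and analyses it by "Analysis of Covariance (ANCOVA) adjusting for baseline nodule hardness".

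**The concern.** Every Part 1 participant should have a hardness and size reading from the same nodule two weeks before the outcome reading. The Part 1 analysis text makes no stated use of it. The protocol accepts baseline adjustment for hardness in Part 2, where the groups are large, and leaves it out where they are smallest.

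Two things are at stake. First, precision: if readings two weeks apart are well correlated, much of the noise in a two-week comparison can be removed at almost no cost. Second, the form of the estimate: the text allows either a difference in two-week means or a difference in mean change. In cohorts of eight these can differ noticeably, and the choice would be made after the data are seen. These are also the only Part 1 data on the measure that becomes the Part 2 primary outcome.

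**Working it through.** **Inputs from the documents**
- 6 active and 2 placebo per cohort; three initial cohorts, so 18 v 6 overall; at most 40 participants (Protocol sections 6, 8.4, 11.3).
- Hardness SD 8, from 25 pilot patients with early disease (Protocol section 4, Table 2; reused in 11.3).
- A 5-point difference at 12 months, the Part 2 target (Protocol 11.3).

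**Assumptions**
- SD 8 is carried over to Part 1, which enrols established disease. SD 6 and 10 are also tried.
- 5 points is used only as a yardstick, because Part 1 states no target for hardness or size.
- The baseline to two-week correlation r is not given; 0.3 to 0.9 is tried.

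**The plan's own figure.** The only calculation with a hardness effect and SD is for Part 2: 2 × (1.96 + 1.28)² / 0.62² gives 55 per arm; 55 / 0.8 gives 69; total 138, as stated. Unrounded, 5/8 = 0.625 gives 54, then 68, total 136. The Part 1 figure of six per dose rests on in vitro α-SMA and states no alpha or power, so it says nothing about hardness.

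**Chance baseline difference.** SE = SD × √(1/n₁ + 1/n₂); P(gap > 5) = 2 × [1 − Φ(5/SE)].
- One cohort, 6 v 2: 8 × √(1/6 + 1/2) = 6.53; 5/6.53 = 0.765; P = 44% (31% at SD 6, 54% at SD 10).
- One dose v placebo pooled over three cohorts, 6 v 6: SE 4.62; P = 28%.
- Overall, 18 v 6: 8 × √(1/18 + 1/6) = 3.77; 5/3.77 = 1.33; P = 19%.
- Overall at the maximum of 40, 30 v 10: SE 2.92; P = 9%.

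**Gain from adjustment.** ANCOVA SE = plain SE × √[(1 − r²)(1 + 1/(f − 2))], where f is the residual degrees of freedom before the covariate is added. The table gives the SE, with the approximate 95% half-width (t × SE) in brackets.

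| Comparison | No baseline | r = 0.3 | r = 0.5 | r = 0.7 | r = 0.9 |
|---|---|---|---|---|---|
| Stand-alone cohort, 6 v 2 (f = 6) | 6.53 (16.0) | 6.97 (17.9) | 6.32 (16.3) | 5.22 (13.4) | 3.18 (8.2) |
| One model, placebo kept by cohort (f = 18) | 6.53 (13.7) | 6.42 (13.6) | 5.83 (12.3) | 4.81 (10.1) | 2.93 (6.2) |
| One model, placebo pooled (f = 20) | 4.62 (9.6) | 4.53 (9.5) | 4.11 (8.6) | 3.39 (7.1) | 2.07 (4.3) |
| Overall, 18 v 6 (f = 22) | 3.77 (7.8) | 3.69 (7.7) | 3.35 (7.0) | 2.76 (5.7) | 1.68 (3.5) |

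In the one-model rows the SE falls by about 2%, 11%, 26–27% and 55% at r = 0.3, 0.5, 0.7 and 0.9. A simulation of the 24-participant design agrees. The drop in half-width from 16.0 to 13.7 without any baseline term comes from sharing the residual variance across cohorts, and is a separate gain.

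**Why the unstated form matters.** A change score has SE = plain SE × √[2(1 − r)]. At 6 v 2 that is 7.73, 6.53, 5.06 and 2.92 at r = 0.3, 0.5, 0.7 and 0.9. It is worse than the plain two-week mean below r = 0.5 and better above it.

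**Nodule size.** The documents give no SD and no target difference, so nothing can be computed.

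**The case against.** Four objections have force.

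- **A reader might infer that the plan has chosen unadjusted two-week means.** The text does not go that far. One sentence covers all continuous outcomes, including tissue mRNA, which has no pre-treatment value, and it leaves open whether hardness is analysed as the two-week value or as change. The defect is an unspecified form with no stated adjustment. In addition, Protocol section 11 defers full details to a SAP, and the SAP versions issued before the restriction to Part 2 are not among the documents. They may have said more.
- **A reader might infer that baseline imbalance swamps the effect sought.** Part 1 states no effect sought for hardness or size. The 5 points belong to early disease at 12 months after up to four injections, and SD 8 also comes from early disease. Part 1 looks at established disease two weeks after one injection. The figures are benchmarks only.
- **A reader might infer that the results would be biased, or mostly reflect which nodules were harder at the start.** Allocation is randomised, so chance imbalance is already counted in the confidence interval. Baseline accounts for r² of the unadjusted error variance: 25% at r = 0.5 and 49% at r = 0.7.
- **The binding limit is two placebo participants per cohort.** Adjustment does not cure that. With placebo kept by cohort, the half-width still exceeds 5 points at r = 0.9, and ANCOVA fitted to one cohort alone loses precision at r = 0.3.

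It is also fair to say that these are secondary outcomes, and that the Protocol bases the Part 2 dose on other indications rather than on Part 1 hardness. All of this limits the size of the point. None of it supplies the missing specification, and the loss at low correlation does not arise in a single model over all cohorts.

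**Conclusion.** The point holds as a loss of precision and an unspecified estimate for two Part 1 secondary outcomes. Neither the Protocol nor the SAP outline states change from baseline or baseline adjustment for hardness or size, although both readings are scheduled and Part 2 adjusts for baseline hardness.

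At an assumed SD of 8, a chance hardness gap above 5 points arises in 44% of 6 v 2 comparisons and in 19% of overall 18 v 6 comparisons. The benefit of adjusting depends on an unknown correlation: worthwhile at 0.7 or above, modest at 0.5, negligible at 0.3. Nothing can be quantified for size. The documents do not support a claim of bias, nor a comparison with a Part 1 target effect, since none is stated. The Part 1 primary outcome is unaffected.

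**What to change.** In Protocol 11.2 (Part 1) and its copy in SAP Appendix 2, state that nodule hardness and each ultrasound size measure will be analysed by ANCOVA:
- the outcome is the two-week value and the pre-injection value is the covariate;
- one model is fitted over all cohorts;
- the text says whether placebo is pooled or kept by cohort. This needs an explicit choice, because section 6 compares the primary outcome with equivalent saline volumes and the volumes differ between cohorts;
- the adjusted difference with 95% CI is reported for each dose and overall, with the per-dose contrasts labelled descriptive.

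The cost is a few sentences and one degree of freedom per outcome. No extra data are needed. If Part 1 has already been analysed, report the adjusted estimates next to those obtained and state which form was used, as Protocol 11.7 requires for deviations.
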